16.1. Monitoring

It is the responsibility of Medtronic to ensure proper monitoring of the study per regulations. Appropriately trained Medtronic personnel or delegates appointed by Medtronic will perform study monitoring at the study center in order to ensure that the study is conducted in accordance with the CIP, the CTA, and applicable regulatory requirements. Medtronic must therefore be allowed direct access to the subject's clinic and hospital records when so requested as per the ICF and CTA.

Monitoring visits could be conducted at the start, during and at the closure of the clinical study in accordance with Medtronic SOPs and the Monitoring Plan. Frequency of monitoring visits will occur based on subject enrollment, study compliance, findings from previous monitoring visits and any suspected inconsistency in data that requires investigation.

The monitoring activities will include at least verification of signed and dated ICFs have been correctly obtained from each subject and that all required study documents are filed into the ISF. Source data verification will be performed as defined in the Monitoring Plan.

16.2. Data Management

The information collected by paper CRFs and reported to Medtronic will be stored in a secure location at the site. The investigator must ensure accuracy, completeness and timeliness of the data reported in the CRFs.

Only authorized persons can complete and sign CRFs, as specified on the Delegated Task list (DTL) included in the ISF.

16.3. Direct Access to Source Data/Documents

The principal investigator(s), his/her delegate(s) and the study coordinator(s) shall be accessible to Medtronic field personnel and the Clinical Study Manager/Scientist. This accessibility is of particular importance for reviewing data in the CRF. Direct access to subject medical files for source data verification will need to be granted and prepared prior to any monitoring visits.

Medtronic may conduct audits at participating investigation sites. The purpose of an audit is to verify the adequate performance of the study related activities. Independent of the employees involved in the study. Regulatory authorities

may also perform inspections at participating investigation sites. Any regulatory authority inspection announcements shall be forwarded immediately to the Study Manager.

The investigator and/or institution shall permit Medtronic and regulatory bodies direct access to source data and documents, taking into account any restrictions due to local law, to perform study-related monitoring, audits, EC review and regulatory inspections.

16.4. Confidentiality

All records and other information about subjects participating in this study will be treated as confidential. The identity of a subject will never be disclosed in the event that study data are published.

Subject confidentiality will be maintained throughout the clinical study in a way that ensures the information can always be tracked back to the source data. For this purpose, a unique subject identification code will be assigned and used to allow identification of all data reported for each subject.

Study data may be made available to third parties, e.g. in the case of an audit performed by regulatory authorities, provided the data are treated confidentially and that the subject's privacy is guaranteed. Sites will maintain subject privacy according to local and national regulations and institutional requirements.

16.5. Liability

No subject compensation is forecasted.

16.6. CIP Amendments

If the investigator will propose any appropriate modification(s) of the CIP or investigational device/product or investigational device/product use Medtronic will review this proposal and decide whether the modification(s) will be implemented.

Medtronic will submit any significant amendment to the CIP, including a justification for this amendment, to the appropriate regulatory authorities if applicable and to the investigators to obtain approval from their EC. The investigator will only implement the amendment after approval of the EC, regulatory authority and sponsor. Administrative amendments to the CIP will be submitted to the EC for notification or approval in case the EC policy requires administrative amendments to be approved as well. Furthermore CIP amendment will be executed after investigators signature collection for any approved amendment for agreement.

16.7. Record Retention

The investigator is responsible for the preparation and retention of the records cited below. All of the below records, with the exception of case report forms and source documents, should be kept in the ISF (i.e., the study binder provided to the investigator) or Subject Study Binder. CRFs must be maintained and signed at the site. At a minimum, the following records must be kept by the investigator for a period of two years (or longer as local law or hospital administration requires) after the date on which the investigation is terminated:

- Signed and dated ICF
- Documentation of the dates and rationale for any deviation from the protocol
- Signed and dated CRFs (including AEs, DDs and CRF corrections)
- Subject ID log
- All approved versions of the CIP, ICF
- Signed CTA
- Current signed and dated CV of principal investigators and members of investigation site team included in the delegated task list.
- Documentation of delegated tasks
- Technical Support List
- EC approval documentation. Written information that the investigator or other study staff, when member of the EC, did not participate in the approval process. Approval documentation must include the EC composition
- Study training records for site staff
- Insurance certificates, if required
- List of investigation sites
- Correspondence related to the study
- Name and contact information of monitor(s)
- Reports of AEs and DDs
- Regulatory authority notification, correspondence and approval if applicable
- Accountability logs of sponsor provided devices (if applicable)
- Final Study Report

A copy of the Final Clinical Study Report will be provided by the Investigator to the EC.

Medtronic shall maintain the following accurate, complete, and current records:

- Internal tracking of Medtronic provided devices (if applicable)
- Signed CTA
- Current signed and dated CV of principal investigator and members of the investigation site team included in the delegated task list
- Delegated Task List
- Technical Support List
- All approved ICF versions
- Copies of all EC approval letters and relevant EC correspondence and EC voting list/roster/letter of assurance
- Names of the institutions in which the clinical study will be conducted
- Insurance certificates, if applicable
- Final report of the clinical study
- The approved CIP and any revision
- Study training records for site personnel and Medtronic personnel involved in the study
- Correspondence related to the study
- Name and contact information of monitor(s)
- Statistical Analysis
- Regulatory authority notification, correspondence and approval if applicable
- Monitoring visit reports and relative follow-up letters
- Other study reports
- Signed and dated CRFs, including AE and DD forms, and CRF corrections

After closure of the study, all records and reports will be archived indefinitely.

16.8. Publication and Use of Information

Publications and presentations referring to this clinical study will be coordinated by Medtronic to allow the use of all available data. The following publication policy will have to be adhered to by all participating investigation sites:

Medtronic may intend to publish the results of the study in scientific journals and congresses.

There are no plans to form a publication committee. Publication activities will be assessed after the study is completed and any collaboration with the investigator will be determined at that time.

Authorship on any publication(s) resulting from this clinical study will be assigned according to substantial contributions to conception and design, acquisition of data, or analysis and interpretation of data, drafting the article or revising it critically for important intellectual content, final approval of the version to be published and agreement to be accountable for all aspects of the work in ensuring that all questions related to the accuracy or integrity of any part of the work are appropriately investigated and resolved. This is in accordance with the Vancouver principles (The Uniform Requirements for Manuscripts Submitted to Biomedical Journals: Writing and Editing for Biomedical Publication, Latest ICMJE

Recommendations ("Recommendations for the Conduct, Reporting, Editing, and Publication of Scholarly Work in Medical Journals", 2013), as agreed upon by the editors of all major medical journals.

The number of authors will be dependent on the regulations of the concerning journal.

Based on the principle that Medtronic owns the data of this clinical study, a single investigation site not access and use the data provided by itself for scientific publications unless there is prior approval by Medtronic.

Medtronic as the owner of the data can use the data and/or any results derived from the data or publications based on that data for marketing purposes, further research and development of devices or educational use or submission to Regulatory Authority.

The study sponsor will collect data in such way that no subject can be identified, and monitor study records.

Participating subjects will not be identified by name in any published reports about the clinical study.

16.9. Suspension or Early Termination

Medtronic or Regulatory Authority (if applicable) may decide to suspend or prematurely terminate the clinical study (e.g. if information becomes available that the risk to study subject is higher than initially indicated). If the clinical study is terminated prematurely or suspended, Medtronic shall promptly inform the investigators of the termination or suspension and the reason(s) for this. The investigator shall then promptly inform the reviewing EC and the study subjects and their personal physician.

Medtronic, EC or Regulatory Authority (if applicable) may decide to suspend or prematurely terminate an investigation site (e.g. in case of expiring approval of the reviewing EC, non-compliance to the CIP or lack of enrollment). If an investigation site is suspended or prematurely terminated, Medtronic shall promptly inform the investigator(s) of the termination or suspension and the reason(s) for this. The investigator shall then promptly inform the reviewing EC and the study subjects and their personal physician.

When the risks are found to outweigh the potential benefits or when there is conclusive proof of definite outcomes, investigators must assess whether to continue, modify or immediately stop the clinical study in the respective investigation site and immediately inform the sponsor and EC, if applicable.

In case of early investigation site suspension or termination subjects will be followed-up as per standard of care.

In case of early investigation site suspension or termination the investigator must notify site suspension or termination to EC and Regulatory Authority, if required.

In case of close out, the investigators will be notified and notification/report to Medtronic, EC and Regulatory Authority will be done, if required.

17. References

2. Ellenbogen KA. Pacing therapy for prevention of atrial fibrillation. *Heart Rhythm* 2007;4:S84-87.

| 2.0 | 
Section 3 and 10:
 
Research procedures order changed for subjects in atrial fibrillation after pulmonary vein ablation, first assess potential ventricular capture, then test rapid pacing, next apply cardioversion if needed and finally test pacing characteristics septal electrodes.Figure 1 updated according to new order research procedures. 
Section 10.3:
 
Research procedures order changed for subjects in atrial fibrillation after pulmonary vein ablation, first assess potential ventricular capture, then test rapid pacing, next apply cardioversion if needed and finally test pacing characteristics septal electrodes.Added specification to AF cycle length “at maximum output which did not induce ventricular capture (20 mA or lower)” | [name], Clinical Research Manager |
| 3.0 | 
Section 5.1.2
 
Added “rapid pacing phase” to “the two-stage pacing scheme” 
Section 5.2.2
 
“Three different PCL” replaced with “various PCL”Added “if feasible” related to the possibility to perform the slow pacing phase of the two-stage pacing scheme 
Section 7.1
 
Added word “potentially” related to the AF termination 
Section 10
 | [name], Clinical Study Manager |

| | | |
|--|--|--|
| | 
Deleted “in the left atrial appendage”Added “rapid pacing phase” to “the two-stage pacing scheme”“at least a minute” replaced by “half a minute”Added “if feasible” related to the possibility to perform the slow pacing phase of the two-stage pacing scheme and to terminate AF 
Section 10.1
 
Aggregated Adverse Events and Device Deficiencies forms 
Section 10.3
 
“an optimal” PCL replaced by “various PCLs, being percentage of AFCL”“Three different PCL” replaced with “multiple PCL” | |
|--|--|--|

LVESV	Left Ventricular End Systolic Volume
LVEF	Left Ventricular Ejection Fraction
LVESV	Left Ventricular End Systolic Volume
MEC	Medical Ethics Committee
PIC	Patient Informed Consent
RA	Right Atrium
RBBB	Right Bundle Branch Block
RV	Right Ventricle
SADE	Serious Adverse Device Effect
SAE	Serious Adverse Event
SAP	Statistical Analysis Plan

4. Introduction

Pacemaker-based therapy for atrial fibrillation (AF) has been discussed as an alternative to drugs and ablation for patients with a conventional indication for pacing. (Redfearn and Yee 2006) (Ellenbogen 2007) Today, many pacemakers and implantable defibrillators include pacing algorithms developed for the prevention or the termination of AF. (Redfearn and Yee 2006) Most existing pacing algorithms have a preventive nature, designed to suppress AF triggers and to reduce the dispersion of atrial refractoriness that predisposes to re-entry (Ellenbogen 2007). Preventive pacing algorithms are primarily designed to decrease premature atrial contractions and prevent pauses, but results of clinical trials with these algorithms have been mixed, probably because of the differences in study design, pacing algorithms and patient populations. (Knight, Gersh et al. 2005) (Carlson, Ip et al. 2003) (LUIGI, HELMUT et al. 2003) (Gold, Adler et al. 2009) Anti-tachycardia pacing (ATP) algorithms designed to terminate atrial tachycardia's deliver pacing bursts at a cycle length shorter than that of the detected arrhythmia. (Redfearn and Yee

2006), (Ellenbogen 2007) While successful ATP could be observed in terminating atrial flutter or organized atrial tachycardia's, it has proved difficult to interpret the results from clinical studies evaluating ATP for AF. (Redfearn and Yee 2006), (Gillis, Koehler et al. 2005), (Gulizia, Mangiameli et al. 2006) Therefore, the evidence of treating AF by pacing is limited, although these algorithms are of interest, since they appear to be safe and usually add little additional cost. (Knight, Gersh et al. 2005) (Gold, Adler et al. 2009).

5.1 Primary Objective

The primary objective of the study is to evaluate the feasibility to obtain a stable position of a ring of stimulation electrodes on the interatrial septum.

5.2 Secondary Objectives

The secondary objectives of this study are:

- Localized Atrial Capture: evaluate if during the rapid pacing phase of the two-stage septal pacing scheme (rapid pacing followed by a step-wise transition to slow-pacing) from multiple electrodes on the interatrial septum, local atrial capture can be observed during atrial fibrillation.
- AF Termination Scheme: evaluate if AF termination can be obtained using a dual-stage septal pacing scheme (rapid pacing followed by a step-wise transition to slow-pacing) from multiple electrodes on the interatrial septum.

6. Investigation Plan

The AF Septal Pacing study is a non-randomized, non-controlled, acute, single-arm research study that will be conducted in up to three European centers.

Approximately 15 subjects with AF indicated for ablation of the pulmonary vein will be enrolled in the study. Participants will attend the Baseline visit and the Procedure visit that can occur on the same day. Since it is an acute study, no follow-up visit will occur. The research procedure will be performed during an already scheduled ablation procedure.

The point of enrollment is the time when subject signs and dates the Informed Consent Form (ICF). At that point, the subject is considered included in the study.

Selection of subjects, treatment of subjects, and evaluation of study data are potential sources of bias. Methods incorporated in the study design to minimize potential bias include (but are not limited to):

- Patients will be screened to confirm eligibility for enrollment in accordance to the inclusion/exclusion criteria.
- Subject demographics will be collected at baseline on possible differences that may affect the primary objective.
- All study clinicians, participating site personnel, and Medtronic personnel will be trained on their respective pertinent role of the study using standardized training materials.

No control group, no randomization and no blinding will be used in this Study.

Clinical Study Flowchart is summarized in Figure 2:

[figure not shown]

Figure2: Standard ablation procedure (left side) and experimental procedure (right side, yellow boxes) performed during standard procedures.

6.1 Inclusion Criteria

All below inclusion criteria must be met:

- Patient referred to the center to undergo ablation of the pulmonary vein using radiofrequency (initial AF ablation or redo procedure).
- In case of paroxysmal AF, the right atrium should be dilated as indicated by $> 29 \text{ ml mm}^2$ or the left atrium should be dilated as indicated by $> 34 \text{ ml mm}^2$.
- Patient is willing and able to cooperate with the study procedure.
- Patient is willing to provide the Informed Consent for their participation in the study.

6.2 Exclusion Criteria

None of the below exclusion criteria must be met:

- Patients under 18 years or over 80 years old.
- Women who are currently pregnant or have a positive pregnancy test.
- Patients with an implantable cardiac device
- Patients who already underwent an AF septal ablation procedure.

7. Determination of Sample Size

As this is a feasibility study, no formal statistical hypotheses are being tested and no sample size calculation was performed.

8. Statistical Methods

8.1 Study Subjects

8.1.1 Disposition of Subjects

The subject disposition will be described in terms of: number of patients enrolled, number of patients undergoing the study stability test, number of patients undergoing the overdrive stimulation test, patients completing the study.

8.1.2 Clinical Investigation Plan (CIP) Deviations

Any deviation(s) from the original statistical plan will be described and justified in the final report.

8.1.3 Intention to Treat Dataset

The “intention to treat” (ITT) dataset will be the primary dataset for patient baseline and safety related reporting. All patients that meet the study inclusion and exclusion criteria, that signed the informed consent, and underwent the clinically indicated ablation procedure are part of the intention to treat dataset. Patients that did not undergo the ablation procedure are not part of the intention to treat dataset.

8.1.4 Per Protocol Dataset

The “per protocol” (PP) dataset will be the primary dataset for the analysis of the primary and secondary study objective. All patients where the septal lead was placed, and the septal pacing threshold test was performed are part of the per protocol dataset. Patients remain in the per protocol dataset if no high rate overdrive pacing was performed.

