5.2. Endpoints

5.2.1. Primary Endpoint

To assess Pacing Site Stability, the number of interatrial septal pacing electrodes which are successfully placed in a stable position, will be counted. A stable position in this study is defined as a location where the pacing threshold will be < 10 mA at a pacing pulse width of 1 msec. Stable pacing further requires that no ventricular capture will be induced during atrial stimulation at twice the atrial capture threshold.

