10.3. Assessment of Efficacy

During sinus rhythm, the number of cases in which the septal pacing electrodes are successfully placed in a stable position will be registered. A stable position is defined as a location where the atrial septal pacing threshold is lower than 10 mA at 1msec on all electrodes and where no ventricular capture at twice the atrial capture threshold is observed.

When the subject is in sinus rhythm after PV ablation, as a first step the atrial pacing threshold is determined, for each electrode, using a pulse width of 1 msec. Also, the impedance is determined for each electrode. During atrial stimulation at high threshold currents, ventricular capture may be possible and absence of ventricular capture at the atrial capture threshold measurement will be confirmed by stimulating from each electrode with twice the atrial capture threshold current (corresponding to specific electrode) from all electrodes at the same time using overdrive pacing at 20 bpm. If ventricular capture is observed during atrial stimulation at twice the atrial capture threshold, the position of the catheter on the septum will be changed and the tests for measuring thresholds, impedances and ventricular capture will be repeated until no ventricular capture occurs during atrial pacing at twice the atrial capture threshold. If it does not occur we will increase the current up to 20 mA and repeat sequence mentioned above. The maximum current will be that current, which does not induce ventricular capture when stimulating from all four electrodes at same time and is 20 mA or lower.

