14.2. Patients sets considered for the analysis

The analysis set will include all enrolled patients matching inclusion/exclusion criteria (Intention to Treat).

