8.1.5 Clinical Investigation Plan (CIP) Deviations

8.2 General Methodology

Data analysis will be performed on the final frozen set of data. Data will be read only for the analysis, and data will not be modified during analysis. Analysis code will be written, appropriately documented, and version controlled. Analysis code will be kept together with the data analysis. Analysis code will be validated before final analysis. Missing data will be included in the analysis. No imputation of missing data will be done.

Data will be displayed graphically as single or multiple (for subgroups) box plots.

All statistical analyses will be performed using R – language and environment for statistical programming and graphics (version 3.X) or alternatively other accepted statistical software.

Subject data listings and tabular and graphical presentations of analysis results will be provided.

Analysis of all safety related data, including study deviations and adverse events will be based on the “intent to treat” (ITT) principle and dataset.

Analysis of all primary, secondary objectives will be done on the per protocol data set; patient data will be summarized for the per protocol data set as well.

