8.7 Evaluation of Objectives

The primary objective is purely descriptive. The per protocol dataset will be used for evaluation of the primary and secondary objective. Reporting on primary and secondary objective will be initially done for the full protocol dataset. Pre-defined subgroups will be described including the following: Per Center analysis, per initial arrhythmia, per septal lead, per patient mode (unipolar vs. bipolar).

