8.7.1 Primary Objective

The primary objective of the study is to evaluate the feasibility to obtain a stable position of a ring of stimulation electrodes on the interatrial septum (stability performance).

Specifically, this primary objective of stable position of a ring of stimulation electrodes on the atrial septum also includes pacing threshold, pacing impedance, stability criterion and safety criterion variables. These data will be summarized in table format as count of data, count of missing data, mean, median, standard deviation, minimal and maximal values for continuous variables, and count of data and count of missing data, number and percentage per category, for categorical data.

∴

Description of stability performance assessed on *per patient basis* includes:

- Description of overall stability criterion (pacing threshold < 10 mA) (categorical variable)
- Description of the number of electrode pairs reaching the stability criterion;
- Description of safety criterion (no ventricular capture) (categorical variable)
- Description of the number of electrode pairs reaching the safety criterion

Description of stability performance assessed on *electrode pair basis*:

- Description of the pacing threshold (continuous variable)
- Description of the pacing impedance (continuous variable)
- Description of stability criterion (pacing threshold < 10 mA) (categorical variable)
- Description of safety criterion (ventricular capture) (categorical variable)

○

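### The SAP's per-protocol set leaves patients whose septal placement failed before threshold testing out of the primary feasibility percentage

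*SAP*

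**What the plan says.** Protocol 14.2 defines one analysis set: "The analysis set will include all enrolled patients matching inclusion/exclusion criteria (Intention to Treat". The protocol's stability measures are counts. In 5.2.1, "the number of interatrial septal pacing electrodes which are successfully placed in a stable position, will be counted"; in 10.3, "the number of cases in which the septal pacing electrodes are successfully placed in a stable position will be registered".

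The SAP defines two sets.

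- **ITT (8.1.3).** Eligible, consented and ablated: "Patients that did not undergo the ablation procedure are not part of the intention to treat dataset". It is the main set for baseline and safety reporting.
- **Per protocol (8.1.4).** "All patients where the septal lead was placed, and the septal pacing threshold test was performed are part of the per protocol dataset".

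The primary objective goes to the second set. SAP 8.2 states "Analysis of all primary, secondary objectives will be done on the per protocol data set" and SAP 8.7 states "The per protocol dataset will be used for evaluation of the primary and secondary objective". No ITT or sensitivity version of the primary result is planned.

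SAP 8.7.1 describes stability per patient as a categorical variable, reported as number and percentage. It adds "Description of the number of electrode pairs reaching the stability criterion". SAP 8.3 excludes missing data and plans no imputation.

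**The concern.** The objective is to find out whether a stable position can be obtained, and getting the ring placed is part of that. SAP 8.1.4 makes placement and testing a condition for being counted. A patient in whom the ring could not be placed, or placement was abandoned before a threshold was measured, is a failure on the primary question but does not appear in the primary percentage. The reported figure then describes patients who got as far as testing, and feasibility looks better than it was.

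The protocol and the SAP also name different analysis sets for the same objective, and the SAP does not explain the change. With no hypothesis test and about 15 subjects, the descriptive percentage is the main finding, and one patient moves it by almost 7 points (1/15 = 6.7%).

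**Working it through.** **No stated figure to reproduce.** Protocol 14.1 and SAP 7 give no hypothesis, target rate or sample size calculation.

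**Inputs**

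- Planned number: about 15 (Protocol 6, SAP 6).
- Replacement to at least 15 complete datasets when missing data would significantly affect the objectives (Protocol 8.1).
- k, the number of attempts that fail before testing: not in the documents. Assumed to be 0 to 3.
- All subjects are taken as eligible, ablated and attempted, so that the Protocol 14.2 set, the SAP ITT set and the attempted set coincide.

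**Direction.** Let n be the number tested and s the number of those found stable. The SAP rule gives s/n; counting failures as not stable gives s/(n + k). The difference is

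s/n − s/(n + k) = s·k / [n(n + k)],

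which is never negative and is zero when k = 0.

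**Size, 15 attempts, all tested patients stable** (exact Clopper-Pearson 95% intervals)

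| k | SAP rule | All attempts |
|---|---|---|
| 0 | 15/15 = 100% (78.2–100) | 15/15 = 100% (78.2–100) |
| 1 | 14/14 = 100% (76.8–100) | 14/15 = 93.3% (68.1–99.8) |
| 2 | 13/13 = 100% (75.3–100) | 13/15 = 86.7% (59.5–98.3) |
| 3 | 12/12 = 100% (73.5–100) | 12/15 = 80.0% (51.9–95.7) |

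**Size, failures replaced until 15 are tested, all stable.** This assumes that a failed placement is treated as missing data under Protocol 8.1. The SAP rule gives 15/15 = 100% (78.2–100) throughout.

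| k | All attempts |
|---|---|
| 1 | 15/16 = 93.8% (69.8–99.8) |
| 2 | 15/17 = 88.2% (63.6–98.5) |
| 3 | 15/18 = 83.3% (58.6–96.4) |

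**Some tested patients unstable.** With 15 attempts, k = 2 and two tested patients unstable, the SAP rule gives 11/13 = 84.6% against 11/15 = 73.3%. The gap is 11.3 points, compared with 13.3 when all tested patients are stable.

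**Thresholds missing for another reason.** Under Protocol 10.3, a subject still in AF has thresholds measured only once in sinus rhythm. If sinus rhythm is not restored, the threshold is missing without placement having failed. Take 15 attempts with 2 placement failures, 1 such missing threshold and 12 stable:

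- SAP rule: 12/12 = 100%.
- Missing subject left out: 12/14 = 85.7% (57.2–98.2).
- Missing subject counted as not stable: 12/15 = 80.0% (51.9–95.7).

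**Stable pairs per patient.** Assuming four pairs in every stable patient and k = 3, the mean is 4 × 12/12 = 4.0 under the SAP rule. Over all attempts it is 4 × 12/15 = 3.2, or 4 × 15/18 = 3.3 with replacement. The total number of stable electrodes is the same under either rule.

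**The case against.** The strongest reply is that the dataset is not the only cause. If the SAP used the Protocol 14.2 set, a patient without a threshold would still drop out as missing under SAP 8.3. This stands: changing the set is not enough, and a rule that scores failed placement as not stable is needed as well. It does not rescue SAP 8.1.4, which removes the patient before any scoring rule could apply.

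Other points have weight.

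- **The protocol gives counts, not a percentage.** Correct. The documents conflict over the analysis set, and the affected percentage is the SAP's own. The protocol's raw counts do not change.
- **Few patients may be affected.** Patients tested and found unstable stay in. Because the protocol provides for repositioning and a second catheter, many poor positions will show up as a high threshold. Only failures before testing are lost, and there may be none. Whether a patient in whom no electrode captured counts as tested is open to reading.
- **The loss is visible.** Disposition counts (SAP 8.1.1), subject listings (SAP 8.2), missing-data counts (SAP 8.3) and deviation reports (Protocol 10.6) would show it. None of them enters the primary percentage.
- **The protocol leaves room for a narrower set.** Protocol 8.1 speaks of complete analyzable datasets for the stability analysis, and Protocol 14.8 lets deviations be justified in the final report. Neither gives a reason for dropping failures on the endpoint itself, and a justification after the data are seen is weaker than one written beforehand.
- **The study is descriptive.** True, and no stated decision depends on the figure. That limits the severity but does not remove the bias.

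**Conclusion.** The concern holds. Followed as written, SAP 8.1.4, 8.2 and 8.7 exclude placement failures before testing from the primary feasibility percentage, and from any mean of stable pairs per patient. This can only favour feasibility. The size depends on a failure count that the documents do not give: zero with no such failure, and 6.7, 13.3 or 20.0 points for 1, 2 or 3 failures in 15 attempts when all tested patients are stable. The gap is somewhat smaller when some tested patients are unstable. No direction is claimed for thresholds missing for reasons unrelated to placement. It should be corrected before analysis; it does not invalidate the study, because no success criterion rests on the figure.

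**What to change.** Amend SAP 8.1.4, 8.2 and 8.7 as follows.

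1. Make the primary denominator all eligible, ablated subjects in whom septal placement was attempted, meaning that positioning of the septal catheter on the interatrial septum was started for the study. State and justify the difference from Protocol 14.2.
2. Score a subject as not stable, with 0 stable pairs, if the ring could not be placed or no electrode captured after an attempt.
3. If the threshold is missing for a reason unrelated to placement (for example, sinus rhythm not restored or time ran out), report the subject as missing with the reason. Show the percentage with these subjects counted as not stable and with them left out.
4. List never-attempted subjects with reasons, outside the denominator.
5. Keep an attempted subject in the denominator even if replaced under Protocol 8.1.
6. Keep the per-protocol result as supportive.
7. As a minor wording point, reconcile SAP 8.2, which includes missing data, with SAP 8.3, which excludes them. For example: missing values are counted and shown, never imputed.

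**Cost.** SAP wording, with no extra patients. SAP Table 3B has a StablePosition field (yes, no, na) that can hold the outcome. Tables 1B to 6 have no field for placement attempted or failed, so attempt status and the reason for a missing threshold may have to come from procedure records. The reported rate may be less favourable, and two percentages are needed if any threshold is missing for an unrelated reason.
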